3.1 Main objective

To evaluate, at 6 weeks after the end of the treatment, the efficacy of tacrolimus nasal ointment on the duration of nosebleeds when administered for 6 weeks in patients with HHT complicated by nosebleeds.

3.2 Secondary objectives

The secondary objectives are to evaluate:

4. Tolerance of tacrolimus nasal administration for 6 weeks, throughout the study.

5. Efficacy of the treatment on progress in the

- clinical parameters:
 - Nosebleed duration,
 - Number of nosebleeds,
 - Number of transfusions of red blood cells.
 - Quality of life
 - ESS = Epistaxis Severity Score

- biological parameters: hemoglobin and serum ferritin concentrations

These parameters will be evaluated at the end of the 6 weeks of treatment (V2) and at the end of 6 weeks of follow-up (V3).

6. Systemic absorption after nasal administration.

4 Methodology

4.1 Outline of the experiment

This is a multicenter, randomized study carried out in double blind. For all patients, monitoring will be for 12 weeks (6 weeks' treatment + 6 weeks' follow-up).

4.1.1 Monitoring the patients

The tacrolimus ointment will be delivered at the centers participating in the study during the first visit after verifying the inclusion criteria. A phone call is scheduled on day 31, i.e. 30 days after the beginning of the treatment, to monitor the safety of the treatment. Patients will have two medical visits: at the end of the treatment and after 6 weeks of follow-up.

A scientific committee and an independent monitoring committee will be set up (see paragraph 12.1 & 12.2).

A specific management procedure is envisaged for each expected complication (see paragraph 7.3).

4.1.2 Patient selection

Patients in the HHT network will thus be informed of the study in progress during a standard ENT consultation or in the Reference Center or Skill Center.

Patients will be included (the consent form will be signed) on the day of the treatment is prescribed.

Subjects will be attributed a number in relation to their chronological inclusion.

4.1.3 Duration of the study

The duration of the inclusion period will be maximum 18 months.

The duration of participation per patient will be 12 weeks (6 weeks' treatment + 6 weeks' of follow-up).

The total duration of the study will thus be maximum 21 months.

[figure not shown]

Figure 6: Schedule

4.2 Patients

4.2.1 Recruitment and feasibility

Aspects to ensure the feasibility of the project

- Network coordinated by the reference center (over 2000 patients followed regularly). The cohort of patients followed for HHT in the Lyon reference center is around 1,000 patients. At the national level, more than 2,000 patient files are currently included in the database. Of these patients, at least 25% present with nosebleeds that justify ENT management.
- The complication targeted by the treatment (epistaxis) is frequent, present in 95% of patients over the age of 50.
- Previous studies conducted by the Reference center, including Metafore published in 2012,¹ Ellipse published in 2014⁶⁵ and Alegori published in 2016⁶³.
- The support of the patients' association (AMRO) and the high expectations of the patients.

4.2.2 Number of patients

We intend to randomize 48 patients.

4.2.3 Modalities for recruitment, inclusion and follow-up

Recruiting and informing the patients of the study in progress will take place during a standard ENT consultation or in the Reference Center or Skill Center for HHT.

Patients will be included on the day the treatment is prescribed.

The treatment is self-administered by patients, twice daily, for 6 weeks.

The follow-up period will be scheduled as follows:

- at each consultation, an ENT examination and a clinical examination including measurement of heart rate and blood pressure will be performed

[figure not shown]

Figure 7: Diagram of the running of the study

4.2.4 Inclusion criteria

- Age ≥ 18 years.
- Patients who have given their free, informed and signed consent.
- Patients affiliated to a social security scheme or similar.
- Patients monitored for clinically confirmed HHT (presence of at least 3 Curaçao criteria) and/or confirmed by molecular biology.
- Patient presenting nosebleeds with total duration > 30 minutes for 6 weeks prior to the time of inclusion justified by completed follow-up grids.

4.2.5 Exclusion criteria

- Women who are pregnant or nursing (lactating), women of child-bearing potential without reliable contraception.
- Patients not affiliated to a social security scheme.
- Patients who are protected adults under the terms of the law (French Public Health Code).
- Refusal to consent.
- Patients for whom the diagnosis of HHT has not been confirmed clinically and/or by molecular biology.
- Participation in another clinical trial which may interfere with the proposed trial (judgment of the investigator).

- Patients who have undergone nasal surgery in the 6 weeks prior to inclusion.
- Known hypersensitivity to macrolides in general, to tacrolimus or to any of the excipients.
- Patient with an inherited skin barrier disease such as Netherton's syndrome, lamellar ichthyosis, generalized erythroderma, graft-versus-host skin disease, or suffering from generalized erythroderma.
- Patient with CYP3A4 inhibitors treatment, e.g. erythromycin, itraconazole, ketoconazole and diltiazem.
- Patients who have incompletely filled in the nosebleed grids in the 6 weeks preceding the treatment. If there is missing data for more than 7 days (10%), the patient cannot be included.
- Patients who do not present nosebleeds with a total duration of > 30 minutes for 6 weeks prior to the time of inclusion.
- Patients with ongoing immunosuppressive treatment
- Patients with known and symptomatic immune deficiency.

4.3 Assessment criteria for the study product

4.3.1 Main judgement criterion

The main judgement criterion is the percentage of patients experiencing an improvement in their nosebleeds. An improvement is defined as a 30% reduction in the total duration of nosebleeds over 6 weeks after treatment, compared with the duration of the nosebleeds in the 6 weeks before the treatment.

4.3.2 Secondary judgement criteria

1. Adverse Events (AE) and Severe Adverse Events (SAE) observed throughout the study (clinical examination, epistaxis grids, ENT examination at each visit before and after the treatment). Additionally, all patients are contacted by phone after 15 and 30 days of treatment in order to collect data on tolerance and observance of the treatment.
2. Clinical efficacy criteria:
 - Nosebleed duration will be evaluated by the nosebleed monitoring grids completed by the patient (Appendix 1), collected at inclusion (V1): observation of the nosebleeds in the 6 weeks prior to inclusion, at the end of the treatment (V2): observation of the nosebleeds in the 6 weeks during treatment, and at the end of the study (V3): observation of the nosebleeds in the 6 weeks after the end of the treatment.
 - Progress in the number of nosebleeds. This criterion will be evaluated by the nosebleed monitoring grids completed by the patient (Appendix 1) collected at inclusion (V1): observation of the nosebleeds in the 6 weeks prior to inclusion, at the end of the treatment (V2): observation of the nosebleeds in the 6 weeks during treatment, and at the end of the study (V3): observation of the nosebleeds in the 6 weeks after the end of the treatment.
 - Comparison of the number of red blood cell transfusions between inclusion (V1) (collected over 6 weeks before treatment), the end of the treatment (V2) (collected over 6 weeks of treatment) and at the end of the study (V3) (collected over 6 weeks after the end of the treatment).
 - Progress in the scores obtained in the SF36 quality of life questionnaire

completed at inclusion (V1), at the end of the treatment (V2) and at the end of the study (V3).

- Progress in the ESS (Epistaxis Severity Score) using data from the specific questionnaire (Appendix 2) completed at inclusion (V1), at the end of the treatment (V2) and at the end of the study (V3).

Biological efficacy criteria: progress in hemoglobin and serum ferritin concentrations between inclusion (V1) and the end of the treatment (V2) and at the end of the study (V3).

3. Systemic absorption, after 1, 3 and 6 weeks of nasal administration, will be evaluated by a tacrolimus dosage in the blood at the end of the treatment.
Blood samples on EDTA are sent to the laboratory for a centralized analysis. A specific procedure is established to maintain the blind: the analysis results will not be transmitted as the study is ongoing, but may be provided on request at the end. Investigator will be informed in case of dosage above 5 ng/mL.

If convenient, patients can connect to the Clinsight platform (Ennov Clinical), with a personal identification number, and complete on-line questionnaires (ESS and SF36) and epistaxis grids. Otherwise they will complete a paper form.

4.4 Randomization, blinding and lifting the blind

The randomization process will be centralized. Allocation of a randomization arm to a patient included will be made by IWRS (Interactive Web Response System), on the basis of a unique randomization list for all investigation centers.

The lists of randomization will be pre-established, by the “Pole IMER” at the Hospices Civils de Lyon – Clinical Research Unit.

Clinsight (Ennov clinical) software will be used to manage this study.

During the inclusion visit, after verifying the inclusion criteria, the investigator connects to the platform to include the patients in the eCRF. This will assign an identification number. When inclusion is validated, the patient is randomized and a treatment code is allocated by the system. The treatment is then dispensed by the pharmacy at the Hospital Center.

This will be a double blind study in which neither the patient nor the investigator will be aware of the nature of the treatment administered so as to annul any bias in the follow-up and measurements.

Tubes of Tacrolimus 0.1% or placebo will be identical and will have appropriate labeling.

Should a serious adverse event occur, the main investigator, the co-investigators or the sponsor may request that the Anti-Poison Center in Lyon lift the blind 24h/24h (the phone number is written on the clinical trial participation card). The written detailed procedures for lifting the blind will be given to the investigators and the Anti-Poison Center in Lyon.

All requests for unblinding must be justified. Most often, study drug discontinuation and knowledge of the possible treatment assignments are enough to treat a study patient who presents with an emergency condition. When the investigator asks for unblinding, he/she must provide patient identifying information, the date, and the reason for unblinding. The investigator will be informed of the details of the drug treatment.

4.5 Modalities for premature termination of the treatment and withdrawal from the study

If the treatment is prematurely or temporary stopped by the patient:

- Due to complications linked to the product: intolerance or discomfort, the patient will not be replaced and will be followed-up as initially planned for the study.
- Due to intercurrent events such as high temperature, rhinitis, etc. the patient may start ointment administrations again when the event turns out favorably and will be followed-up as initially planned for the study.
- Due to reasons other than the onset of complications linked to the drug, such as for logistical reasons (for example, a patient's work-related trips), the patient will not be replaced and will be followed-up as initially planned for the study.

If a visit following treatment is not attended by the patient and cannot be rescheduled, this visit will be considered as absent and the next post-treatment follow-up visit will be scheduled according to the original timetable initially devised for this patient. There is no maximum number of post-treatment follow-up visits missed after which the patient will be withdrawn from the study, particularly in the case of complications.

4.6 Rules for definitive termination

4.6.1 A research person terminates his or her participation in the study

A patient's participation in the study will be terminated should the patient withdraw his or her consent. Patients may withdraw their consent at any time in the course of the study. Their withdrawal from the research does not in any way change their relationship with the investigating doctor, who will propose medical follow-up that is adapted to their clinical condition.

Patients will also stop the study treatment if they undergo nasal surgery or other procedures (such as local hemostatic matrix), as this may modify interpretation of the results. However, their follow-up will be maintained.

4.6.2 Termination of all or part of the research

The research may be terminated either temporarily or definitively:

- by decision of the main investigator, the sponsor or the Competent Authority;
- in case of knowledge of data that could compromise the study for reasons concerning the safety of the patients;
- in case of publication of new scientific data that bring the research into question.

5 Description, supply and management of the drugs

5.1 General modalities of preparation and administration

Marketed Protopic® 0.1% tubes of 30 g are used for this study. For the placebo, the manufacturing and filling is managed by an external pharmaceutical laboratory with GMP agreement. The placebo formulation is similar to the active ointment; it contains all the ingredients except the active one: tacrolimus. The product is provided in strictly identical tubes. The same masked label is placed on both batches in order to respect the blind.

The ointment is self-administered by patient, twice daily, for 6 weeks.

5.2 Treatment tested

The treatment tested is tacrolimus, manufactured by the laboratories Astellas and commercialized as Protopic® (tube of 30 g) at 0.1% of tacrolimus.

5.2.1 Modalities for the preparation

Commercialized tubes (30 g) of Protopic® 0.1% are used. Tubes are completely masked by a specific label. This process will be carried out by Unither pharmaceuticals, a Contract Manufacturing Organization located in Bordeaux (France).

An additional label is attached with suitable information regarding the clinical trial, including the treatment code allocated. This labeling will be carried out by the Pharmacy at the Hospices Civils de Lyon. The tubes will be weighed before delivery to the patient.

5.2.2 Storage and conservation

The shelf life of the product is two years.

Tubes should be stored at room temperature, not above 25°C.

5.2.3 Return and destruction

After the end of the administration period, the tubes will be returned to the pharmacy at the hospital center and will once again be weighed "after administration" so as to determine the exact quantity administered. The tubes will be conserved for the monitoring visits and destroyed in accordance with the procedures in force after sponsor authorization.

5.3 Placebo

The comparative treatment is the same formulation as the active product but without tacrolimus.

5.3.1 Modalities for preparing

This product is manufactured for this study by Unither pharmaceuticals, a Contract Manufacturing Organization located in Bordeaux (France). The ointment is packed in strictly identical tubes to those of Protopic®, and covered by the masking label.

An additional label is attached with suitable informations regarding the clinical trial, including the treatment code allocated. This labeling will be carried out by the pharmacy at the Hospices Civils de Lyon. The tubes will be weighed before delivery to the patients.

5.3.2 Storage and conservation of the placebo

The shelf life of the product is two years.

A certificate is provided by Unither pharmaceuticals, according to stability study results. The tubes should be stored at room temperature, not above 25°C.

5.3.3 Return and destruction

After the end of the administration period, the tubes will be returned to the pharmacy and will once again be weighed "after administration" so as to determine the exact quantity administered. The tubes will be conserved for the monitoring visits and destroyed in accordance with the procedures in force after authorization.

5.4 Associated treatments

No other experimental drug for nosebleeds may be used during the study. If nasal surgery becomes necessary during the study, the patient will be withdrawn from the study.

Systemically available tacrolimus is metabolized via hepatic Cytochrome P450 3A4 (CYP3A4). The possibility of interactions cannot be ruled out and patients with ongoing treatment of CYP3A4 inhibitors (e.g. erythromycin, itraconazole, ketoconazole and diltiazem) will not be included in the study.

All other concomitant treatments necessary for management of the patient will be authorized during the study and will be documented in the study's data collection sheets. Recommendations will be given to patients in case of administration of another nasal treatment (see paragraph 6.2.1).

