9.2.1 Analysis populations

9.2.1.1 “Efficacy” population in intention to treat

This population will be composed of all the randomized patients. If patients stop the study treatment, their follow-up will be maintained in order to obtain the epistaxis grids.

9.2.1.2 “Efficacy” population per protocol

This population will be composed of all the patients who have received all the treatments set out in the protocol. A treatment will be considered complete if the patient received at least a total of 60 administrations out of 84 (twice a day for 42 days) envisaged by the protocol.

9.2.1.3 “Safety” population

This population will be composed of all the patients who have received at least one ointment.

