9.2.2.4 Analysis of the main judgement criterion

The percentage of patients experiencing improvement in their nosebleeds will be computed in each group. An improvement is defined as a 30% reduction in the total duration of nosebleeds over 6 weeks after treatment, compared with the duration of the nosebleeds in the 6 weeks before the treatment.

The percentage of the two groups will be compared using a Fisher exact test, and the analysis will be performed on the intention to treat population.

Patients who stopped the treatment but who have epistaxis grids will be analyzed using their data. Patients who withdraw from the study before completing the follow-up will be considered as failures.

A descriptive listing will present for each patient: the duration of nosebleeds before treatment, during treatment, after treatment, the treatment group, the number of consecutive days of treatment, the total number of days of treatment.

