9.2.2.6 Handling of missing values/censoring/discontinuations

Follow-up of patients will be pursued regardless of the situation, except if the patient withdraws his or her consent. In the case of nasal surgery during the study period or any other treatment that is a substitute to the studied treatment, the patient will be followed up but his or her results will be considered as a failure.

The main judgement criterion is based on grids that are filled in daily. Patients are used to these grids and fill them in carefully; the daily durations are summarized over 6 weeks. However if one day is missing, the value will be replaced by an average of the 4 values before and the 4 values after the missing value. This strategy will be applied up to 7 missing values over 6 weeks (i.e. 10%).

If more than 7 days and less than 21 days (included) are missing, a daily average will be computed from the data available (from the 6-week period evaluated) and will be multiplied by 42 to obtain the overall estimated duration.

If a patient is lost to follow-up or refuses to communicate his nosebleed grids or has more than 21 days missing on his grids, the result for the concerned patient will be considered as a failure.

10 Quality assurance

The Clinical research associate mandated by the sponsor is responsible for inspecting the case report forms in conformity with the monitoring schedule for the study, throughout the study, verifying that the protocol is being respected, as well as the totality and the conformity of the source documents, the coherence of the data and that the regulations governing good clinical practices are being respected. The Clinical research associate mandated must have access to the medical files of the patients and other files in relation to the study needed to verify the data entered in the study's electronic case report forms.

The controls of presence, verisimilitude, and coherence will be carried out electronically in accordance with the rules defined in advance. Requests for information will be generated when possible errors are detected.

The health authorities and/or an independent auditor mandated by the sponsor may audit any investigation site, or the sponsor, throughout the duration of the study or after the end of the study so as to control how the study is being conducted and the quality of the data. The investigator must provide direct access to the source documents, and the sponsor to the regulatory documents.

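### Section 5.4 takes nasal-surgery patients out of the study while 4.6.1 and 9.2.2.6 keep them in follow-up, which puts secondary and some late safety data at risk

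*Combined protocol and SAP*

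**What the plan says.** Four places in the combined protocol and SAP bear on a patient who has nasal surgery or stops the study treatment.

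- Section 5.4 (Associated treatments): "If nasal surgery becomes necessary during the study, the patient will be withdrawn from the study".
- Section 4.6.1 (ending of a participant's involvement): "Patients will also stop the study treatment if they undergo nasal surgery or other procedures", and then: "However, their follow-up will be maintained".
- Section 9.2.2.6 (missing values and discontinuations), on surgery or a substitute treatment: "the patient will be followed up but his or her results will be considered as a failure". The same section opens with a general rule: "Follow-up of patients will be pursued regardless of the situation, except if the patient withdraws his or her consent".
- Section 9.2.1.1 (intention-to-treat population): "If patients stop the study treatment, their follow-up will be maintained in order to obtain the epistaxis grids".

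Section 9.2.2.4 adds a rule for the primary analysis: "Patients who withdraw from the study before completing the follow-up will be considered as failures".

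**The concern.** Section 5.4 cannot be applied together with the other three. The wording is not idle, because the protocol treats stopping treatment and leaving the study as different things. Section 4.5 names both in its title. Section 9.2.2.4 analyses patients who stop treatment on their own grids but scores those who withdraw as failures. A site could therefore reasonably read 5.4 as the end of visits and grids, while another site following 4.6.1 carries on. Inclusion takes place at three centers, so practice could differ between them.

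What is at stake is the data after surgery. Surgery in the treatment period would cost the V2 and V3 values under 5.4; surgery in the follow-up period would cost V3. A patient whose nosebleeds lead to surgery is not missing at random in any obvious sense, and data not collected at the time cannot be recovered later.

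**Working it through.** **1. Is it the same event?** Yes. Sections 5.4, 4.6.1 and 9.2.2.6 all name nasal surgery during the study. Section 5.4 ends participation; the other two continue follow-up. The general rule in 9.2.2.6 allows one exception only, withdrawal of consent, and surgery is not that. Section 9.2.1.1 does not name surgery, but it covers any stop of study treatment, which 4.6.1 says surgery entails.

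**2. Does the primary endpoint change?** No. Under 4.6.1 and 9.2.2.6 the patient is followed and scored as a failure. Under 5.4 the patient leaves before completing follow-up and is a failure under 9.2.2.4. The classification is the same.

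**3. Does the sample size change?** No. The inputs from section 9.1 are 60% against 15% improved, two-sided alpha 5%, 80% power and the Fisher exact test. Exact power is the sum, over all pairs (x, y), of Bin(x; n, 0.60) × Bin(y; n, 0.15) for tables with a two-sided Fisher p-value of at most 0.05.

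- n = 21 per arm: 0.799
- n = 22 per arm: 0.827
- n = 24 per arm: 0.876

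The stated 22 per arm is reproduced. The step from 44 to 48 allows for a loss of 1 − 44/48 = 8.3%. Nothing here depends on which surgery rule applies, since these patients count as failures either way.

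**4. Which analyses are exposed?** Section 9.2.2.5 compares changes from V1 to V2 and from V1 to V3 in nosebleed duration, number of nosebleeds, transfusions, SF36, ESS, hemoglobin and ferritin. It uses t-tests or Mann-Whitney tests, plus mixed models. A patient taken out has no later value for these tests. The grid-replacement and failure rules in 9.2.2.6 are built around the primary criterion, and failure has no defined value for a continuous outcome. The mixed models would use earlier values, but they do not remove bias if the missingness depends on bleeding that was not observed.

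**5. Which safety data are exposed?** Section 9.2.2.5 lists adverse events from inclusion to the end of follow-up. Sections 7.2.1 and 7.2.3 set their own recording window, to 30 days after the last administration, with fatal and related events after that. Section 7.2.4 follows events to resolution or stabilization, and 7.4.2 prolongs ENT monitoring after a septal perforation. Section 7.2.2 separately stops recording once a new out-of-study treatment starts. Only part of the later safety data therefore hangs on 5.4.

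**6. How large could it be?** The documents give no surgery rate, so the following are assumptions.

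If 1 to 6 of the 48 patients had surgery, 1/48 = 2.1% to 6/48 = 12.5% would lose later secondary data under 5.4.

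For the effect on an arm of 24, let m be the full-arm mean V3 duration, k the number of patients lost, and r their bleeding as a multiple of m. The mean of those remaining is m(24 − kr)/(24 − k).

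- r = 3, k = 1: 21/23 = 0.913, a shift of about −9%
- r = 3, k = 2: 18/22 = 0.818, about −18%
- r = 0.5, k = 1: 23.5/23 = 1.022, about +2%
- r = 0.5, k = 2: 23/22 = 1.045, about +5%

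The sign turns on whether r is above or below 1. This is the raw V3 mean. The planned tests use change from baseline, and a rank test does not move in proportion to the mean, so these figures show scale only.

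**The case against.** The strongest reply is that 5.4 is one sentence in a section on concomitant treatments and does not say that data collection stops. The section that governs the end of participation deals with surgery directly and keeps follow-up, the analysis section repeats this, and 4.5 takes the same line for the other treatment stops it lists. A careful site would probably follow those. This stands as a reason to think the loss is avoidable and perhaps unlikely. It does not remove the contradiction: the sentence is current text and nothing says which section prevails.

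A reader might also infer more than the documents support:

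- That the heaviest bleeders are lost, and that the arm with more surgery is flattered in every secondary comparison. The documents do not describe who will need surgery. The values that 4.6.1 would retain are post-surgery values, which surgery may lower, and 4.6.1 itself warns that surgery can affect interpretation. The calculation above gives either sign.
- That adverse event collection ends. Sections 7.2.1 to 7.2.4 and 7.4.2 keep part of it whatever 5.4 says, and 7.2.2 could end some of it even if 5.4 were corrected.
- That the intention-to-treat population fails. Section 9.2.1.1 defines it as everyone randomized, so membership is unaffected; only its follow-up sentence conflicts with 5.4.
- That the shift in mean can be read against the 30% criterion. That is a within-patient cut-off for the primary endpoint, which does not change.

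**Conclusion.** The point holds as an internal contradiction with a limited reach. Section 5.4 conflicts with 4.6.1, 9.2.2.6 and the follow-up sentence of 9.2.1.1. The primary classification and the sample size of 22 evaluable, 24 planned per arm are untouched. If a site acts on 5.4, the V2 and V3 secondary outcomes and some late safety data are lost for patients whose absence is related to their clinical course.

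The direction and size of any resulting bias are unknown. The range of about −9% to +2% for one patient lost from an arm of 24 rests on assumed post-surgery bleeding of three times and half the arm mean. The number of such patients is also assumed. The case for acting is that arms are small, the lost data cannot be recovered, and the correction costs almost nothing. It is not that a bias in a known direction has been shown.

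**What to change.** Reconcile 5.4 with 4.6.1, 9.2.1.1 and 9.2.2.6 so that one rule applies at all sites, and word 5.4 so that it separates stopping the study treatment from ending data collection. This takes one sentence in 5.4. The visits, grids, questionnaires and blood samples are already scheduled, and neither the sample size nor the primary analysis changes. The request concerns consistency of data collection and takes no position on clinical management.

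The reconciliation leaves two matters open, which can be settled in the same revision: how post-surgery values enter the continuous secondary analyses, since 9.2.2.6 speaks only of failure, and whether surgery counts as a new out-of-study treatment for the adverse event cut-off in 7.2.2.
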